8 DATA COLLECTION

Please see section 7.2 above for measurements and time points.

The medical history, cognitive assessment, and structured questionnaire for symptoms and adverse events will be obtained from the patient in person (and medical notes where necessary) and by telephone by the study researcher after appropriate training as required and entered into the electronic case record form. These researchers will also measure blood pressure, obtain blood samples for haematology and biochemistry as necessary (analysed in the hospital NHS haematology or biochemistry labs in the centre in which the patient has been recruited).

The researcher at each site will co-ordinate the appointment for one year MRI. A reminder that the MRI appointment is due will be sent by the Trial Co-ordinating Centre. The MRI will be performed in approved radiology departments using sequences specified for the trial.

All baseline medical, cognitive, scanning and laboratory data will be entered into a secure password protected electronic case record form (eCRF) run from the University of Nottingham, accessible to approved research staff for data entry. The data from central reading of MRI will be added to the eCRF data for statistical analysis. Participant and relative/carer contact details, required to perform Trial follow-up, will be stored in an encrypted secure password-protected database also provided by the University of Nottingham, separate to the Trial eCRF database, and only accessible to selected researchers in the Trials Unit, University of Edinburgh and the University of Nottingham.

Paper versions of the CRF (i.e. source data sheet) will be available to assist with data collection when interviewing patients at baseline and during follow-up visits in phone or in person. Paper CRFs will be filed in the patient's paper-based folder and held in a secure locked filing cabinet at site.

The MR or CT brain images obtained at diagnosis of the stroke and 1 year follow-up MRI will be anonymised and sent to Edinburgh where they will be assessed and quantified for the index stroke, features of small vessel disease and other features, using validated scores and volume measurements by an experienced rater. Images will only be identified by study ID.

Questionnaires will be checked for completeness and any queries resolved by phone. Telephone follow-up will be used to minimise missing data. All paper forms will be stored in a secure locked facility after data have been entered onto the eCRF.

9 STATISTICS AND DATA ANALYSIS

9.1 SAMPLE SIZE CALCULATION

There are few data on which to base sample size. There is little experience with cilostazol in Europe or North America, and little experience with ISMN in this group of patients in the UK (or in any patients with stroke). We have been guided by colleagues in Japan where cilostazol is in common use and there is experience with it in stroke. The main purposes of the trial are to assess tolerability and safety.

Table 6 Annual absolute risks (%) of outcome events after lacunar stroke

Vascular death	Non-vasc death	Non-fatal isch stroke or TIA	Non-fatal ICH	MI	MACE	Dependent (mRS 3-5)	Any cogn impt.	Dementia
1.8	0.5	2.5	0.5	0.6	3	15	30	15

We calculated mean annual event rates (Table 6) from trials (SPS3,³³ lacunar patients in ENOS⁵⁰ IST-3,⁶³ of cilostazol, Figure 1) and observational data (LADIS;⁶⁴ our^{4, 65} and other⁶⁶

studies). We expect deaths including vascular deaths of median 2.0% p.a., with 4% being the upper 95% CI of 2% in 400 patients.³³ LACI-2 therefore has a sample size of 400.

For a main Phase III trial, recurrent stroke 2.5%pa, MI 0.6%pa and vascular death 1.8%pa,^{4, 33} (MACE) are infrequent; new cognitive impairment c16% at one year,^{6, 66} dependency 15%, are frequent and important to patients, justifying their inclusion in a composite primary outcome. However, these event rates are imprecise with wide ranges; more precise estimates are needed. We estimate main Phase III trial sample size at 1100 (Table 7), assuming 80% power, alpha 5%, 10% loss to follow-up, composite event rate (45%) and conservative estimate of cilostazol effect (20% RRR is the lower 95% CI of effect, Figure 1). A primary outcome including MRI SVD progression (A, below) was considered but at least 15% of patients miss repeat MRI, sample sizes were similar (or larger, due to variance in WMH change⁶⁵ short term), the cost is much higher and the WMH intermediary measure is less relevant to patients.

Table 7. Sample size for composite outcome in main trial, estimated event rates.

Composite model	A	B	Ci	Cii	D
Composite outcome for Phase III includes:	MACE, dementia, non-vasc death, new MR signs	MACE, dementia, death	MACE, cog↓, dependency↓, death		MACE, cog imp, depend, all death
1-beta (power)	80%	80%	80%	80%	80%
Event rate, control, pa	50%	10%	30%	30%	45%
Relative risk reduction	20%	20%	20%	30%	20%
Event rate, active, pa	40%	8%	24%	21%	36%
Total sample size	950	6626	1784	778	976
Total trial size, inc losses	1250	7400	2000	900	1100

Assume: 1:1 randomisation and Fleiss adjustment; alpha 5%; primary outcome incomplete in 10%

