2.2.2 Secondary Endpoints

Tolerability - 75% of patients will be able to tolerate trial medication, in at least half dose, up to one year after randomisation (i.e. less than 25% will stop trial medication completely through inability to tolerate the drugs).

Safety - symptoms of systemic or intracranial bleeding, recurrent cerebral and systemic vascular events, and vascular and non-vascular causes of death will be collected. The absolute risk of death, including fatal haemorrhage, will not differ significantly (ie fall outside the upper 95% CI) from 2% per year on trial drugs versus no trial drugs, when given in addition to guideline drugs; and will not increase bleeding or ischaemic SVD lesions significantly (at the p<0.01 level) on MRI.

Efficacy – individual event-rate data (stroke, TIA, myocardial ischaemia, cognitive impairment and dementia, will be collected. The *combined rate* of recurrent stroke, MI, death, cognitive impairment and dependency will be 40-50% at one year after enrolment in order to detect modest but clinically-important reductions in poor outcomes.

Health Economics – data to assess health economic impact will be gathered.

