8b Secondary Objectives: To assess drug tolerability, safety, recruitment rates and accuracy, outcome event rates and retention in preparation to a large phase III randomised controlled trial to prevent recurrent lacunar stroke and physical and cognitive impairment.

This SAP focuses on these primary and secondary objectives. Planned follow-on publications will address tertiary questions.

SECTION 3. STUDY METHODS

9 Trial design

Prospective randomised open-label blinded end-point (PROBE) partial-factorial phase IIb/c trial aiming to recruit 400 patients recruited in UK Stroke Network Centres, with follow-up to one year.

10 Randomisation: By central computer-generated allocation at the University of Nottingham with minimisation on key prognostic factors: age, sex, stroke severity (NIHSS), dependency resulting from the stroke, systolic blood pressure $\leq/ > 140$ mmHg, smoking status, time after stroke, and years of education.

11 Sample size/power considerations

Conservatively, we have used sample size calculations based on binary measures. Use of ordinal measures at the time of analysis will increase statistical power.

11a Event rates: Annual event rates (Table A) were assessed from trials (SPS3,⁵ lacunar patients in ENOS,^{6 7} IST-3^{8 9}) and observational data (LADIS;¹⁰ our¹¹⁻¹³ and other¹⁴ studies). All-cause death rates were assumed to be 2.0% with upper 95% CI of 4% in 400 patients.⁵ Hence, the sample size was set at 400 participants.

Table A Annual absolute risks (%) of outcome events after lacunar stroke

Vascular death	Non-vascular death	Non-fatal IS or TIA	Non-fatal ICH	MI	MACE	Dependent (mRS 3-5)	Cognitive impairment	Dementia
1.8	0.5	2.5	0.5	0.6	3	15	30	15

ICH: intracerebral haemorrhage; IS: ischaemic stroke; MACE: major adverse cardiac events; MI: myocardial infarction; mRS: modified Rankin scale; TIA: transient ischaemic stroke

11b Comparison of two groups in a future phase III trial: Assuming power 0.80, alpha=0.05, 1:1 randomisation, composite event rate (MACE, dementia, non-vascular death, new MRI signs) 45% and absolute reduction 9% (relative risk reduction 20%), and loss to follow-up 10%, a sample size of 1100 will be needed. A

number of outcomes are relevant to patients with SVD and using these has implications for the sample size (Table B).

Table B. Sample size for composite outcome in main trial using estimated event rates.¹

Composite model	A	B	Ci	Cil	D

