- Recruitment of sufficient patients, i.e. 400 patients in 24 months in the UK (and taking account of interruption due to COVID-19).
- >95% of randomised patients are retained for follow-up at one year.

Secondary outcomes - participant

Tolerability: 75% of patients will be able to tolerate trial medication, in at least half dose, up to one year after randomisation (i.e. less than 25% will stop trial medication completely through inability to tolerate the drugs).

Safety

- Symptoms of systemic or intracranial bleeding.
- The absolute risk of death, including fatal haemorrhage, does not differ significantly, i.e. fall outside the upper 95% CI of 2% per year on trial drugs versus no trial drugs, when given in addition to guideline stroke prevention drugs.
- There are no new ischaemic or haemorrhagic brain lesions or increase in SVD lesions on one year MRI significantly (at the p<0.01 level).

Efficacy

- Individual event-rates for stroke, TIA, myocardial ischaemia, cognitive impairment and dementia.
- The *combined rate* of recurrent stroke, MI, death, mild cognitive impairment (including dementia), dependency and new stroke lesions on scanning at 1 year will be 40-50% at one year after enrolment in order to allow detection of a modest but clinically-important reduction in poor outcomes in a phase III trial.
- Health economic measures include the health utility score (EQ-5D-5L) and the visual analogue score (EQVAS) at 12 months.

26b Units: Units will be shown in tables.

26c Calculations/transformations: Quality of life using UK weightings.

Brain frailty

Based on neuroimaging:

- Brain frailty = Atrophy + WML + Previous stroke lesion ⁷

- SVD score for CT = WML, lacunes; for MRI includes WMH, lacunes, PVS and microbleeds ¹⁵

Montreal cognitive assessment-modified (MoCA-m) trails

Since Trails A and B are performed, the MoCA trail is not collected but rather estimated from the Trails B score:

- If Trails B score <12 then MoCA trail = 0
- If Trails B score >=12 then MoCA trail = 1

27 Analysis methods

27a Methods

Primary endpoint

- Tabulation and graphical presentation of participant recruitment aiming for 400 participants in 24 months.
- Tabulation of retention of participants at one year aiming for >95%.

Analyses of secondary outcomes

Tabulations of:

- Tolerability to trial medications aiming for 75% of patients taking at least half dose for up to one year after randomisation.

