- Death, including fatal haemorrhage, aiming for less than outside the upper 95% CI of 2% per year.
- The *combined rate* of recurrent stroke, MI, death, cognitive impairment and dependency, aiming for 40-50% at one year after enrolment.

Comparison of rates of events between the treatment groups: cilostazol vs no cilostazol, ISMN vs no ISMN, and cilostazol and ISMN vs neither, for:

- Systemic or intracranial bleeding, recurrent cerebral and systemic vascular events, and vascular and non-vascular causes of death.
- Death, all cause.
- New ischaemic or haemorrhagic stroke lesion or increase in SVD lesions on MRI.
- Composite of: recurrent clinically-evident stroke, MI, death, cognitive impairment (including dementia) and dependency.
- Individual event: stroke (clinically-evident or imaging-detected ischaemic or haemorrhagic stroke to be reported separately), TIA, myocardial ischaemia, cognitive impairment and dementia.
- New infarcts and haemorrhages, absolute and change in WMH, microhaemorrhages, lacunes, atrophy imaging variables from central read of baseline imaging and one year MRI
- The comparisons of combined cilostazol and ISMN versus neither, whilst being very underpowered statistically, are presented since these may be the two groups studied in the planned follow-on trial.

Central tendency, comparisons and regressions will be analysed as follows (**Table D**).

Table D. Descriptive and analytical statistics

	Binary	Nominal	Ordinal	Continuous
Central tendency and distribution	N (%)	N (%)	Median [interquartile range]	Mean (standard deviation)
Comparisons	Chi-square (2x2)	Chi-square (2x2, or rxc)	Mann-Whitney U or Kruskal-Wallis	t-test (pooled) or 1-way ANOVA
Regression	Binary logistic regression (BLR)	-	Ordinal logistic regression (OLR)	Multiple linear regression (MLR)

27b Covariate adjustment: Analyses will be adjusted for minimisation covariates:

- Age, sex, stroke severity (NIHSS), dependency resulting from the stroke, systolic blood pressure, smoking status, time after stroke, years of education.

Covariate adjustment with continuous variables (age, NIHSS, SBP, time after stroke, years of education) will use original, not dichotomised, data.

27c Assumption checking: The assumption of proportionality will be tested using the likelihood test.

27d Alternative methods: If the data fail the assumption of proportionality (tested using the likelihood test), we will use alternative methods such as multiple logistic regression.

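### The 4% upper limit for deaths that sets N=400 is the precision of all arms pooled, not of the drug groups the safety criterion is about; SAP Table 2's <2% target also conflicts with that criterion

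*Protocol*

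**What the plan says.** Protocol 9.1 states "We expect deaths including vascular deaths of median 2.0% p.a", "with 4% being the upper 95% CI of 2% in 400 patients", and concludes "LACI-2 therefore has a sample size of 400". SAP 11a gives the same reasoning: "All-cause death rates were assumed to be 2.0% with upper 95% CI of 4% in 400 patients".

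The criterion this supports is worded by treatment. Protocol 2.2.2 requires that the risk of death should not differ significantly "from 2% per year on trial drugs versus no trial drugs, when given in addition to guideline drugs". SAP 26a says it should not "fall outside the upper 95% CI of 2% per year on trial drugs versus no trial drugs".

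The SAP is less clear on how the criterion is scored. The tabulation in SAP 27a reads "Death, including fatal haemorrhage, aiming for less than outside the upper 95% CI of 2% per year" and names no group. SAP Table 2 has a single column of achieved values. It splits tolerability into ISMN alone, cilostazol alone and both, but has one undivided death row, with a target of <2%.

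Separately, SAP 27a and Table 3 plan comparisons of death for each drug against no such drug and for both against neither. Protocol 9.2 adds Kaplan-Meier and Cox analyses of death.

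**The concern.** A sample size justified by precision should quote the precision of the estimate that will be used. Here the quoted limit belongs to the whole trial, including patients allocated neither drug, whereas the conclusion is about patients allocated a drug. No drug group has 400 patients. A reader of 9.1 would expect a 2% death rate on treatment to be known to within an upper bound of 4%, and it will not be. The gap is widest for the combination, which SAP 27a identifies as a possible arm of the follow-on trial.

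The scoring is also open. A death criterion with no named group, and with two different numerical targets in the same SAP, can be judged met or not met on the same data.

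**Working it through.** **Inputs.** Death rate 2% and N=400 (Protocol 9.1, SAP 11a). Allocation 1:1 for each drug (Protocol 5.5.1), so about 200 on each drug, 100 on both, 100 on neither and 300 on at least one. Recruited 363 (SAP Table 2), giving about 182, 91, 91 and 272. Confidence level 95% (SAP 18), taken as two-sided. The group sizes assume nearly everyone is randomised for both drugs; the partial factorial design will shift them somewhat.

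**Step 1: the plan's figure.** The exact (Clopper-Pearson) upper limit for x deaths in n is the 0.975 quantile of Beta(x+1, n−x). For 8 in 400 it is 3.90%, and the Wilson limit is also 3.90%. Both round to the stated 4%. (The simple Wald limit, 3.37%, does not.)

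**Step 2: the groups in the criterion.** Planned sizes use the exact limit. For 363 recruited, 2% is not a whole number of deaths, so the Wilson limit is used: [p + z²/2n + z√(p(1−p)/n + z²/4n²)] / (1 + z²/n). For n=182 this is (0.0200 + 0.0106 + 0.0229)/1.0211 = 5.24%.

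| Group | Planned n | Exact upper limit | n of 363 | Wilson upper limit |
|---|---|---|---|---|
| All patients | 400 | 3.9% | 363 | 4.0% |
| Any drug | 300 | 4.3% | 272 | 4.5% |
| One drug | 200 | 5.0% | 182 | 5.2% |
| Both drugs | 100 | 7.0% | 91 | 7.4% |

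**Step 3: the two targets.** At 363 patients, <2% means at most 7 deaths (0.02 × 363 = 7.26). A 4% ceiling means at most 14 (0.04 × 363 = 14.52). The table gives the probability of meeting each target with all arms pooled. The scenarios are assumptions, not figures from the documents.

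| True death rates | ≤7 deaths | ≤14 deaths |
|---|---|---|
| 2% in everyone | 0.56 | 0.99 |
| One drug doubles deaths to 4% | 0.15 | 0.86 |
| 4% on any drug | 0.06 | 0.71 |
| Both drugs double risk multiplicatively (2/4/4/8%) | 0.01 | 0.33 |

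**Step 4: the planned comparison of arms.** For 2% against 4% at 200 per group the mean rate is 3%. The null standard error is √(0.03 × 0.97 × 2/200) = 0.01706 and the alternative is √((0.0196 + 0.0384)/200) = 0.01703. Power is Φ[(0.02 − 1.96 × 0.01706)/0.01703] = Φ(−0.79), or about 21% (13% with Fisher's exact test). Power of 80% would need 1,141 per group.

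**Step 5: the 2.0% input.** The components in Protocol Table 6 and SAP Table A sum to 1.8 + 0.5 = 2.3%. Protocol 9.1 calls the table entries means and the 2.0% a median. SAP 11a drops the word median.

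**The case against.** The strongest reply is that death is already to be compared by randomised group. SAP 27a lists all-cause death for all three contrasts, Table 3 has a row for it, SAP 18 promises 95% intervals, and Tables 6a–c and 7a–c show fatal serious adverse events by arm. This stands: the plan does not lack a between-group analysis of death. It leaves the precision quoted in 9.1 and 11a uncorrected, and no power or precision is given for those contrasts.

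The most literal reading of the criterion also takes everyone on any drug, where 4.3% is close to the stated 4%. That too is fair. The shortfall is small on that reading and becomes material for a single drug and, above all, for the combination.

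Death is a secondary safety item in a feasibility trial, SAP 27a itself admits that the dual comparison has very little power, and the data monitoring committee sees outcomes unblinded. These points limit the consequences but do not resolve the wording.

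A reader might infer something stronger: that safety will be declared from a pooled 4% rule which usually passes a drug that doubles mortality. The documents do not support this. Neither says that 4% is applied to all arms together, and the one pooled entry, in Table 2, carries <2%, under which that scenario would usually fail. Even a pooled 4% rule would pass only about 33% of the time if both drugs doubled risk multiplicatively. Nor is 2.0% against 2.3% an arithmetic error, since a median need not equal a sum of means.

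**Conclusion.** The precision that justifies N=400 is not the precision of any drug group in the criterion. At a 2% death rate the upper limit is about 4.3% on any drug, 5.0% on one drug and 7.0% on both, rising to about 4.5%, 5.2% and 7.4% at the 363 recruited. These figures assume 1:1 allocation with nearly full factorial randomisation, and two-sided 95% limits.

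Separately, the <2% in Table 2 cannot stand beside the upper-limit criterion in SAP 26a and 27a. With a true rate of 2% and no drug effect, it would be missed about 44% of the time (1 − 0.56). Both statements are in the SAP, so the rule in SAP 4c that the SAP overrides the protocol does not settle which applies.

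How often a pooled 4% rule would pass a harmful drug is conditional on a rule the documents do not state and on assumed effects, so it illustrates the ambiguity and is not a property of the plan.

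**What to change.** - In Protocol 9.1 and SAP 11a, state that 4% is the precision of all 400 patients pooled, and give about 4.3% for any drug, 5% for one drug and 7% for both.
- In SAP 27a and Table 2, score the death criterion by randomised group with exact 95% intervals, next to the between-group comparisons already planned in SAP 27a and Table 3.
- Reconcile the <2% in Table 2 with the upper-limit criterion in SAP 26a and 27a, so that one target applies.
- In SAP 11a, note that 2.0% is a median and that the component means in Table A sum to 2.3%.

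The cost is wording and a few table cells; no new data are needed. The stated precision becomes less favourable. Scoring by drug does not make the trial large enough to exclude a doubling of deaths (about 21% power at 200 against 200), so a non-significant difference should be reported with its interval and not as evidence of safety.

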9.2 PROPOSED ANALYSES

We will compare cilostazol v no cilostazol, ISMN v no ISMN, cilostazol and ISMN v neither. The proportion completing to target dose and any adverse events will be assessed using odds ratios. The LACI-2 will focus on numbers recruited, retained, tolerance and safety outcomes, blinded for TSC and unblinded intention to treat (ITT) for DMC. Safety analysis will use: Kaplan-Meier and Cox proportional regression for analysis of time-to-event outcomes of death; binary logistic regression for SAEs, recurrent stroke, MI, and in those completing 12 month MRI, the amount of microbleeds, siderosis, new infarcts, WMH burden; all adjusted for minimisation variables to maximise power.⁶⁷ We will collect data for future health economics analysis (EQ-5D-5L, EQ-VAS).

A secondary ITT analysis will be performed using logistic regression adjusted for minimisation variables of cilostazol+/-ISMN versus control on efficacy and safety outcomes, with secondary tests of subgroup interactions. Ordinal logistic regression will be used for ordinal categorical outcomes (e.g. mRS) to increase power.⁶⁸

A Statistical Analysis Plan (SAP) will be published prior to database lock and will describe analysis procedures and procedures for missing, unused or spurious data, and definitions of populations analysed.

